10.2.5 Permission Allocation

The system administrator will create accounts for each role and assign specific permissions according to the role requirements.

10.2.6 eCRF Completion

Researchers must collect subject data according to the study protocol and reference the completion guidelines to accurately, promptly, completely, and consistently enter information into the eCRF based on original source data. Any modifications to eCRF data must follow standard operating procedures, with audit trails maintained for all changes.

10.2.7 Query Issuance and Resolution

The Data Management (DM) team will create a detailed Data Review Plan, which must be reviewed and signed off by programmers and the DM project manager (PM) to confirm agreement. After data is entered into the Electronic Data Capture (EDC) system, the system will perform data checks according to the Data Review Plan, using pre-established edit checks to identify data queries automatically. For data that cannot be flagged by automated checks, manual queries will be issued through the EDC. Data entry personnel or researchers must review and respond to both system and manual queries, correcting data if necessary until the query is resolved. If the response does not resolve the query, the data manager and clinical research associate may re-query the data point, with all actions and audit trails recorded in the EDC database.

10.2.8 Data Modification and Review

Data entry personnel or researchers may modify data after verification. For any data modifications, a reason must be provided in the system as prompted. The researcher has the authority to review and approve all final data.

10.2.9 Medical Coding

Medical history and adverse events collected in the study should be coded using standard dictionaries, typically MedDRA and WHODrug Dictionary (WHODD). The

dataset with coded data must clearly document the dictionary and version used for coding.

10.2.10 SAE Consistency Comparison

All SAE-related data points in the eCRF should be programmatically compared with corresponding data points in the Pharmacovigilance (PV) database. Any discrepancies must be discussed with PV personnel and resolved until there are no differences in the data.

10.2.11 Data Review Meeting

Before database lock, the data manager will draft an initial data review report and compile all data listings. The sponsor, researchers, data managers, and statistical analysts will jointly conduct a final review of the database. During this meeting, they will define statistical analysis populations according to the study protocol, verify serious adverse event reports, and review recorded handling information. Following the data review meeting, the finalized data review report and population classification plan resolutions will be documented.

10.2.12 Database Lock and Unlock

Database lock is a key milestone in the study process. The locking process and timing should be clearly documented. Locking restricts edit permissions on the database, preventing any unauthorized accounts from making changes.

If modifications are required after the database is locked, an application must be submitted. The sponsor, researcher, data entry personnel, clinical research associate, and data manager must discuss, approve, and sign off on the request. The reason for unlocking the database must be thoroughly documented.

10.2.13 Data Backup and Recovery

Throughout the data management process in the study, the database should be regularly backed up. In the event of irreparable database damage, the most recent backup should be used for recovery, with any additional data re-entered as needed. The final dataset will be backed up on a read-only CD. All relevant computers must have up-to-date and effective antivirus protection.

10.2.14 Data Storage

During the study, all collected original data (such as eCRF and electronic data) should be securely stored. These original documents are part of the audit trail that traces back to the source data and should be protected with the same rigor as the electronic audit trail, which records any modifications or backups of the database.

10.2.15 Data Confidentiality

Data confidentiality is a fundamental principle in clinical research and development. Organizations involved in drug development should establish appropriate procedures to ensure database confidentiality. This includes creating and signing confidentiality agreements to regulate personnel conduct and implementing security systems to prevent data breaches.

11. Appendix: Adverse Events (AEs) and Serious Adverse Events (SAEs) – Definitions, Severity, and Causality

11.1 Further Details and Explanations on the Definition of AE

Adverse Event (AE): Any unfavorable medical occurrence in a subject after receiving the study product, which may present as symptoms, signs, diseases, or laboratory abnormalities. These events do not necessarily have a causal relationship with the study product.

Pregnancy-related events are not reported as AEs.

11.2 Further Details and Explanations on the Definition of SAE

- The occurrence of herpes zoster (HZ) or postherpetic neuralgia (PHN) does not constitute an SAE.
- Elective surgeries planned prior to subject enrollment are not reported as SAEs.

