2.2.2 Secondary endpoints

Immunogenicity endpoints

- 1) Geometric Mean Concentration (GMC) and seroconversion rate of anti-gE antibodies 30 days after full immunization;
- 2) Geometric Mean Fold Increase (GMFI) in anti-gE antibodies 30 days after full immunization compared to baseline (Day 0).

Safety endpoints

1. Incidence of solicited adverse events (AE) within 0-7 days after each dose, including local (injection site) and systemic (non-injection site) reactions;
2. Incidence of unsolicited AEs within 0-30 days after each dose;
3. Incidence of AEs within 30 minutes after each dose;
4. Incidence of adverse events of special interest (AESIs) from the first dose through 30 days after full immunization;
5. Incidence of serious adverse events (SAEs) from the first dose through 6 months after full immunization.

3. Study design

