5.1.9.2 Follow-up Content

The safety observation content includes all adverse events (AEs) and serious adverse events (SAEs) that occur during the study, such as: pain, pruritus, induration, swelling, rash, redness, fatigue, tiredness, fever, headache, myalgia, etc. It also includes the occurrence of all SAEs and pregnancy events from the first dose of vaccination until six months after the full immunization schedule is completed.

Solicited AEs include:

Injection site (local) AEs	Pain, pruritus, induration, swelling, rash, redness
Non-injection site (systemic) AEs	Fatigue, tiredness, fever, headache, insomnia, myalgia, skin and mucosal abnormalities, pain at non-injection sites, diarrhea, constipation, vomiting, nausea, acute allergic reactions, arthritis, arthralgia

Unsolicited AEs include: Any adverse event that is not a solicited AE or any solicited AE occurring outside the solicitation period (e.g., If the solicited AEs mentioned above occur more than 7 days after vaccination, they should be recorded as unsolicited AEs).

Serious Adverse Events (SAEs)

This study will collect all SAEs occurring from the first dose of vaccination until six months after the completion of the full immunization schedule.

Pregnancy Events

All pregnancy events occurring from the first dose of vaccination until six months after the full immunization schedule will be collected. Details on pregnancy reporting, follow-up, and assessment are provided in Section 7.5.

Specially Monitored Adverse Events

Suspected cases of herpes zoster occurring from the first dose of vaccination until 30 days after the completion of the full immunization schedule will be collected.

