7.4 Adverse events and serious adverse events

7.4.1 Definitions of AE and SAE

Adverse Event (AE): Refers to any undesirable medical occurrence experienced by a subject after receiving the study drug. This can include symptoms, signs, diseases, or abnormal laboratory results, but it does not necessarily have a causal relationship with the study drug.

Serious Adverse Event (SAE): Refers to any adverse medical occurrence experienced by a subject after receiving the study drug, meeting any of the following criteria:

- 1) Results in death;
- 2) Is life-threatening, meaning the subject was at immediate risk of death at the time of the adverse event (not to be confused with potential risks of death if the condition worsens);
- 3) Results in hospitalization or prolongation of an existing hospitalization;
- 4) Results in persistent or significant disability/incapacity;
- 5) Leads to a congenital anomaly or birth defect;
- 6) Other important medical events.

Medical and scientific judgment should be used to decide whether to expedite the report of other situations. Events that may not immediately threaten life, result in death, or require hospitalization but necessitate medical intervention to prevent one of the above outcomes are also generally considered serious.

For further details on AE and SAE definitions, refer to Appendices 11.1 and 11.2.

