7.4.7 Adverse Events of Special Interest (AESIs)

AESIs, specifically suspected cases of herpes zoster, will be collected from the first dose through 30 days after completing the full immunization.

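### Section 11.2 takes herpes zoster and PHN out of the SAE definition with no stated exception, which contradicts the seriousness criteria in 7.4.1 and is not matched in 7.4.8

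*Protocol*

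**What the plan says.** Section 7.4.1 defines an SAE by outcome. One criterion is "Results in hospitalization or prolongation of an existing hospitalization"; others are death, threat to life, and persistent or significant disability. The section ends: "For further details on AE and SAE definitions, refer to Appendices 11.1 and 11.2".

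Section 11.2 then has two bullets. One is "The occurrence of herpes zoster (HZ) or postherpetic neuralgia (PHN) does not constitute an SAE". The other says that elective surgery planned before enrolment is not reported as an SAE. Section 7.4.8, the body-text list of events outside the AE and SAE criteria, names only planned elective surgery and pregnancy.

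The collection windows are:

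- Unsolicited AEs (2.2.2): "Incidence of unsolicited AEs within 0-30 days after each dose".
- Suspected zoster as an AESI (7.4.7): "AESIs, specifically suspected cases of herpes zoster, will be collected from the first dose through 30 days after completing the full immunization".
- Concomitant medication (5.1.10): until 30 days after the last dose.
- SAEs (2.2.2): "Incidence of serious adverse events (SAEs) from the first dose through 6 months after full immunization". Section 5.1.9.2 agrees: "This study will collect all SAEs occurring from the first dose of vaccination until six months after the completion of the full immunization schedule".
- At V8, the Schedule of Activities collects only SAEs and pregnancy events.

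**The concern.** The definition of an SAE feeds a named secondary endpoint and most of the safety-reporting machinery: 24-hour reporting (7.4.4), the sponsor's SUSAR assessment (7.4.5 and 7.4.6) and the SAE content of the DSUR (7.4.9). The suspension and termination criteria for life-threatening or fatal events (6.5, 6.6) and individual emergency unblinding (5.5.3.3) are also worded in terms of SAEs.

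If 7.4.1 and 11.2 give different answers for the same patient, two sites can classify the same hospitalised zoster case differently, and the SAE incidence depends on which section each site follows. Disease events are sometimes kept out of SAE reporting because an efficacy endpoint captures them. This trial has no zoster efficacy endpoint (2.2.1, 2.2.2). Section 1.1 itself says that zoster complications can lead to severe disability.

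**Working it through.** The plan states no figure on this point, so the main check sets the sections side by side. The arithmetic only gives scale.

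**1. One case, two answers.** Take a subject admitted to hospital with zoster.

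| Section followed | Result |
|---|---|
| 7.4.1 (hospitalisation criterion) | SAE |
| 11.2, read literally | Not an SAE |
| 7.4.8 | Silent on zoster and PHN, so no exclusion |

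**2. Does 11.2 leave room for 7.4.1?** Two features of the text point towards the literal reading. First, the elective-surgery bullet beside it plainly overrides the hospitalisation criterion, since planned surgery will often involve admission. Second, the protocol states a return route for pregnancy: sections 7.5.1 and 12.1.3 say pregnancy itself is not an event but its complications are, and may be serious. No section says this for zoster or PHN.

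**3. Where a serious case goes, by time since dose 2.**

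| Route | To day 30 | Day 31 to 6 months |
|---|---|---|
| AESI (suspected zoster) | Collected | Ended |
| Unsolicited AE | Collected | Ended |
| Concomitant medication | Collected | Ended |
| SAE | Closed by 11.2 if read literally | Closed by 11.2 if read literally |

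In the first column the case is recorded but not classed as serious. In the second, no defined collection or analysis route remains.

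**4. Scale of the later window.** Inputs: 300 subjects (5.5.1); a month is 30 days (Definitions of Terms), so 6 months is 180 days and the window is 180 − 30 = 150 days; background incidence 5 per 1000 per year at age 50–59 and 10 per 1000 at 60 and over (1.1).

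- Person-time: 300 × 150/365 = 123.3 person-years.
- All zoster, no vaccine effect, no dropout: 123.3 × 0.005 = 0.62 to 123.3 × 0.010 = 1.23 cases.
- With the 97.2% reduction that 3.2.1 credits to the control vaccine, and none for LZ901: 61.6 person-years per arm gives 0.31 to 0.62 in the LZ901 arm, plus 61.6 × 0.028 × 0.005 to 0.010 = 0.01 to 0.02 in controls, about 0.32 to 0.63 in total.
- With the 10% dropout of 8.2, all assumed lost before the window, the first range becomes 0.55 to 1.11.

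These figures count all zoster. The protocol gives no hospitalisation rate. If a share *s* of cases is serious, the expected number is *s* × 0.62 to *s* × 1.23: for an assumed *s* of 0.1, 0.06 to 0.12; even for an assumed *s* of 0.5, 0.31 to 0.62.

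**The case against.** The strongest reply is that 11.2 speaks of the *occurrence* of zoster or PHN. That can mean that the diagnosis alone is not serious, with the outcome criteria of 7.4.1 still applying. The section is headed as further explanation, not as an override, and 7.4.8 does not exclude zoster. Section 11.1 is equally blunt about pregnancy-related events, although 7.5.1 brings complications back in, so a flat appendix sentence does not prove intent. This much stands: a reader might infer a deliberate ban on ever reporting hospitalised zoster as serious, and the document does not establish one. What remains is that the milder meaning is written nowhere, so the sections conflict as they read.

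A reader might also infer that a late case leaves no trace at all. That goes too far:

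- Lesion sampling of suspected cases has no time limit (3.1.1.2).
- Section 5.1.9.2 opens with a general reference to all AEs and SAEs during the study.
- Subjects are told to call at once about events needing hospitalisation (5.1.8).
- An AE that began inside the window is followed until it resolves or improves (7.4.3).
- Deaths have their own reporting duty (7.4.4).
- The neurological, ocular and vascular complications listed in 1.1 are not named in 11.2 and can be reported as SAEs in their own right.

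None of these, however, is a defined collection or analysis route for new zoster or PHN after day 30.

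Finally, one might call the AESI window too short. Sections 2.2.2, 5.1.9.2, 7.4.7 and 8.4.4 state it consistently, and this is an immunogenicity comparison with no efficacy objective. The window is a design choice, not an error.

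**Conclusion.** The contradiction between 11.2 and 7.4.1 is real, and 7.4.8 does not match 11.2. Applied literally, 11.2 removes a zoster or PHN case that meets a seriousness criterion from the SAE endpoint over its whole period and from the reporting that runs on SAEs. From day 31 after dose 2 it also leaves the case without a defined route.

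The size is small. Expected serious cases in the later window are well below one, given that serious cases are only a part of at most about 0.6 to 1.2 zoster cases. That upper range assumes no vaccine effect and no dropout. It should not be read as a count of missed serious events: it counts all zoster, and non-serious cases after day 30 would go uncollected even with 11.2 corrected. The primary immunogenicity analysis, sample size and non-inferiority comparison are untouched.

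This should be fixed because an SAE definition must give one answer for one patient, not because many cases are expected.

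**What to change.** Reconcile 11.2 with 7.4.1 and 7.4.8. The 11.2 bullet could read: *HZ or PHN is not by its occurrence alone an SAE; it is reported as an SAE when it meets any criterion in 7.4.1.* Section 7.4.8 should then carry the same statement, or refer to it, so that the list in the body and the appendix agree.

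The cost is one sentence in 11.2 and a matching line in 7.4.8, with a note to sites. No visit, sample or analysis is added, because SAE contact to V8 already takes place. Extending AESI collection to V8 would also pick up non-serious late cases. It is optional, is not needed to remove the contradiction, and would require the AESI window to be changed wherever it is stated.

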11.3 Severity

The severity of adverse events following vaccination is assessed according to the Guidelines for Grading Adverse Events in Preventive Vaccine Clinical Trials, issued by the NMPA on December 31, 2019. Adjustments have been made to the grading criteria based on the characteristics of subjects in this study. The grading standards for adverse event severity are as follows:

Tanble 4 Grading table of adverse events at inoculation site (local)

Symptom/Sign	Grade 1	Grade2	Grade3	Grade4
Pain				
Pain	Minimal or mild discomfort, no impact on limb activity	Affects limb activity	Affects daily life	Loss of basic self-care or hospitalization
Induration*, Swelling** (Optional) #				

>14 years	Diameter 2.5–<5 cm or area 6.25–<25 cm ² , no impact on daily life	Diameter 5–<10 cm or area 25–<100 cm ² , no impact on daily life	Diameter ≥10 cm or area ≥100 cm ² or causes symptoms such as restricted limb movement, lymphadenopathy, or drainage affecting daily life	Blistering, ulcerative dermatitis, necrosis, or deep tissue necrosis
Erythema*, Redness** (Optional) #				
>14 years	Diameter 2.5–<5 cm or area 6.25–<25 cm ² , no impact on daily life	Diameter 5–<10 cm or area 25–<100 cm ² , affects daily life	Diameter ≥10 cm or area ≥100 cm ² or associated symptoms affecting daily life	Blistering, ulcerative dermatitis, necrosis, or deep tissue necrosis
Other				
Itching	Itching at the injection site that relieves within 48 hours after self-care or treatment	Itching at the injection site that does not resolve within 48 hours after treatment	Affects daily life	NA
Cellulitis	NA	Need for non-injectable treatment (e.g. oral antibacterial, antifungal, antiviral)	Intravenous therapy is required (e.g. intravenous antibacterial, antifungal, antiviral)	Sepsis, or Tissue Necrosis, etc.

Notes:

* In addition to grading based on direct diameter measurements, the progression of measurement results should also be recorded.

** The maximum measured diameter or area should be used.

The grading of induration and swelling, as well as rash and erythema, should be based on functional impact and actual measurements, with the higher grading criterion being selected.

Table 5 Grading of Vital Signs

Vital Sign	Grade 1	Grade 2	Grade 3	Grade 4
Fever (Axillary Temperature, °C)				
>14 years	37.3~<38.0	38.0~<38.5	38.5~<39.5	≥39.5, lasting more than 3 days

Table 6 Systemic (Non-Local) Adverse Event Grading

Organ System / Symptom	Grade 1	Grade 2	Grade 3	Grade 4
Gastrointestinal System				
Diarrhea	Mild or transient, 3–4 times/day, loose stools, or	Moderate or persistent, 5–7 times/day, loose stools, or	≥7 times/day, loose stools, or resulting in severe symptoms such as hypotension,	Life-threatening, requiring hospitalization

	mild cramping lasting ≤1 week	cramping lasting >1 week	electrolyte imbalance, dehydration, or needing IV fluids >2L	
Constipation*	Requires stool softeners or dietary adjustment	Requires laxatives	Needs manual disimpaction or enemas	Severe toxicity causing intestinal obstruction
Dysphagia	Discomfort with swallowing solids	Limited to soft diet	Limited to liquid diet, cannot tolerate solid foods	Unable to tolerate any oral intake, requires tube feeding
Appetite Loss	Appetite decreases but does not reduce food intake significantly	Decreased intake, significant reduction	Appetite decrease with body weight loss or nutritional decline	Requires nutritional support (e.g., tube feeding or intravenous nutrition)
Vomiting	1–2 times/24 hours, minimal impact on activity	3–5 times/24 hours, activity affected	≥6 times/24 hours or requiring IV fluids	Life-threatening, requires hospitalization or urgent care
Nausea	Mild (<24 hours) with normal food intake	Persistent, affects intake to some extent (24–48 hours)	Persistent nausea limiting food intake ≥48 hours or requiring IV fluids	Threatens life (e.g., risk of aspiration)
Musculoskeletal and Connective Tissue Disorders				
Myalgia (Non-Injection Site)	Does not affect daily activities	Affects daily activities	Severe muscle pain, significantly impacts daily activities	Emergency visit or hospitalization
Arthritis	Mild pain, with swelling, erythema, or joint stiffness, but does not limit function	Moderate pain, with swelling, erythema, or joint stiffness, but does not affect daily activities	Severe pain, requiring analgesics and/or mobility aids, impacting daily activities	Permanent disability or irreversible joint injury
Arthralgia	Mild pain, does not limit function	Moderate pain, may affect function	Severe pain requiring analgesics and/or mobility aids, impacting daily activities	Persistent pain with functional loss
Nervous System				
Headache	Does not affect daily activities, no treatment needed	It is transient and mildly affects daily activities and may require treatment or intervention	Severe, impacts daily activities, requires intensive treatment	Life-threatening, requires emergency care or hospitalization
Syncope	Near syncope, no loss of consciousness (e.g., pre-syncope)	Loss of consciousness, but no intervention required	Loss of consciousness, requires intervention or hospitalization	NA
New-Onset Seizures				

≥18岁	NA	NA	1–3 seizures	Prolonged or multiple seizures (e.g., status epilepticus) or difficult to control (e.g., life-threatening epilepsy)
Respiratory System				
Cough	Transient, no treatment needed	Persistent cough, requires treatment, ineffective	paroxysmal cough, uncontrolled by treatment	Emergency or hospitalization
Acute bronchospasm	Transient, no treatment needed; FEV1% 70–80%	Need medical treatment; Bronchodilator treatment returned to normal; FEV1% is 50% ~ 70%	Bronchodilator therapy does not return to normal; FEV1% is 25% ~ 50% or intercostal depression	Severe, FEV1% <25% or requires mechanical ventilation
Dyspnea (Breathing Difficulty)	Mild, occurs with exertion only	Moderate, occurs with normal activity	Severe, occurs with minimal activity	Life-threatening, occurs at rest
Skin and Subcutaneous Tissue Disorders				
Non-injection Site Rash (No Skin Damage)	Mild itching, does not affect daily life	Itching affects daily life	Severe itching prevents daily activities	NA
Skin/Mucosal Abnormalities	Erythema/itching/color change	Diffuse rash/maculopapular rash/dryness/desquamation	Vesicular/exudation/desquamation/ulceration	Exfoliative dermatitis involving mucous membranes, or erythema multiforme, or suspected Stevens-Johnson syndrome
Nervous System				
Insomnia*	Mild sleep difficulty, no or minimal impact on daily life	Moderate sleep difficulty, affects daily life	Severe sleep disturbance, significant impact on daily life, requires treatment or hospitalization	NA
Irritability/Inhibition	Mild irritability or inhibition	Easily irritable or has difficulty sleeping	Lack of response to external stimuli or low awareness	NA
Psychiatric disorders (including anxiety, depression, mania, and confusion) should report detailed symptoms	Mild symptoms, does not require intervention or minimally affects daily life	With clinical symptoms requiring medical consultation or behavior affecting daily life	Requires hospitalization or inability to perform daily activities independently	Tendency to harm self or others, acute mental confusion, or loss of basic self-care ability
Immune System				

Acute Allergic Reaction**	Localized urticaria (water blisters), no systemic symptoms	Localized urticaria requiring treatment or mild angioedema not requiring treatment	Generalized urticaria or angioedema requiring treatment, or mild bronchospasm	Anaphylactic shock or life-threatening bronchospasm or laryngeal edema
Other				
Fatigue	No impact on daily activities	Affects normal daily activities	Severely affects daily activities, unable to work	Emergency visit or hospitalization
Pain at Non-Injection Sites# (Specify location at reporting)	Mild pain, no or minimal impact on daily life	Pain affects daily activities	Pain preventing daily activities	Disabling pain with loss of basic self-care ability

Notes:

FEV1% refers to the ratio of Forced Expiratory Volume in 1 second (FEV1) to Forced Vital Capacity (FVC).

* Changes in constipation and insomnia before and after vaccination should be monitored.

** Refers to Type I hypersensitivity reactions.

Refers to non-injection site pain other than myalgia, arthralgia, or headache.

For adverse events not covered in the grading tables above, refer first to the Guidelines for Grading Adverse Events in Preventive Vaccine Clinical Trials. If the guidelines do not provide criteria for evaluation, assess the severity according to the following standards.

Table 7 General Grading Criteria for Other Adverse Events

Grade 1	Grade 2	Grade 3	Grade 4	Grade 5
Mild: Short duration (<48h) or slight discomfort, no impact on activities, no treatment required.	Moderate: Moderate or mild impact on activities, may require minimal or no treatment.	Severe: Significant impact on activities, requires intervention, may require hospitalization.	Life-threatening: Potentially life-threatening, severe impact on activities, requires intensive treatment.	Death.

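### Section 11.3 does not give one grade per value for three solicited events: short fever ≥39.5°C, diarrhea at 7 times/day, and nausea at exactly 48 hours

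*Protocol*

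**What the plan says.** Section 11.3 states its basis as follows: "The severity of adverse events following vaccination is assessed according to the Guidelines for Grading Adverse Events in Preventive Vaccine Clinical Trials". It then adds: "Adjustments have been made to the grading criteria based on the characteristics of subjects in this study". The cells that matter are these.

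- **Fever (Table 5, axillary).** Grade 1 is 37.3 to <38.0°C, Grade 2 is 38.0 to <38.5°C and Grade 3 is 38.5 to <39.5°C, none with a duration condition. Grade 4 is "≥39.5, lasting more than 3 days".
- **Diarrhea (Table 6).** Grade 2 begins "Moderate or persistent, 5–7 times/day, loose stools, or"; Grade 3 begins "≥7 times/day, loose stools, or resulting in severe symptoms such as hypotension".
- **Nausea (Table 6).** Grade 1 is under 24 hours, Grade 2 is 24–48 hours with some effect on intake, and Grade 3 is 48 hours or more with limited intake, or a need for intravenous fluids.
- **Vomiting (Table 6), for comparison.** Grade 2 is "3–5 times/24 hours, activity affected" and Grade 3 is "≥6 times/24 hours or requiring IV fluids".

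Two rules might resolve an unclear case. The notes to Table 4 tell the grader to take the higher grade, but only for induration and swelling and for rash and erythema. After Table 6 there is a fallback, first to the guideline and then to Table 7, which opens "For adverse events not covered in the grading tables above".

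Fever, diarrhea and nausea are all solicited systemic events (section 3.1.3.2).

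**The concern.** A severity scale should give each observed value exactly one grade. Here a fever of 39.4°C for one day is Grade 3, while 40.0°C for one, two or three days has no grade, so a higher reading can lose the grade that a lower one receives. For diarrhea and nausea the fault is the reverse: one boundary value satisfies two cells, and the choice is between Grade 2 and Grade 3, which is where the protocol's safety rules draw their line.

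The grades are used. Section 8.4.4 tabulates solicited events by severity in each group, and sections 6.5 and 6.6 count events of Grade 3 or higher for suspending or terminating the study. Section 5.5.3.2 requires unblinding before the second dose, so an ambiguous value after that dose may be resolved by someone who knows the group. Fixed cut-offs would remove that discretion.

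**Working it through.** The protocol gives no figure to reproduce here. The check is to read each cell as a logical condition and count how many grades each value satisfies. Duration is counted in calendar days, which is an assumption.

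**Fever (Table 5)**

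| Axillary temperature | 1 day | 2 days | 3 days | 4 days |
|---|---|---|---|---|
| 37.3°C | 1 | 1 | 1 | 1 |
| 38.0°C | 2 | 2 | 2 | 2 |
| 38.5°C | 3 | 3 | 3 | 3 |
| 39.4°C | 3 | 3 | 3 | 3 |
| 39.5°C | none | none | none | 4 |
| 40.0°C | none | none | none | 4 |

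Section 5.1.9.1 has temperature measured daily from the day of vaccination to day 7 after each dose, so runs of 1, 2 or 3 days at this level would be visible in the diary.

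**Diarrhea, vomiting and nausea (Table 6, on frequency or duration alone)**

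| Event | Value → matching grades |
|---|---|
| Diarrhea, times/day | 3–4 → 1; 5–6 → 2; **7 → 2 and 3**; 8 or more → 3 |
| Vomiting, times/24 h | 1–2 → 1; 3–5 → 2; 6 or more → 3 |
| Nausea, hours | 12 → 1; 24 and 36 → 2; **48 → 2 and 3**; 60 → 3 |

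**Do the other rules settle it?** The higher-grade note in Table 4 does not extend to these three events. The fallback after Table 6 is for events outside the tables, and each of these has its own row. The opening paragraph of 11.3 says the criteria were adjusted for this study, so the guideline cannot simply be assumed to override a row. What the guideline says at these boundaries cannot be seen from the protocol.

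**Size in the severity tables.** With 150 subjects planned per arm, one regraded subject moves that arm's Grade 3 or higher rate by 1/150 = 0.67 percentage points. For scale, section 1.2.2 reports Grade 3 events at 2.01% in the 100 µg group in Phase II; 0.67/2.01 is about one third. The protocol gives no basis for the number of subjects affected.

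**Size in the suspension rule (6.5).** Taking all 300 subjects as the denominator (an assumption), the 15% threshold is 0.15 × 300 = 45 subjects, and one subject is 1/300 = 0.33 points. An event must also fail to drop below Grade 3 within 48 hours. A fever that falls below 38.5°C within 48 hours would not count even after correction, so only fevers persisting beyond 48 hours could matter.

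**After correction.** If Grade 3 also covers ≥39.5°C for 3 days or less, every temperature from 37.3°C upward matches one grade. With diarrhea at 5–6 and ≥7, or at 5–7 and >7, every count from 3 upward matches one grade. With nausea Grade 2 at 24 to <48 hours, 48 hours is Grade 3 only.

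**The case against.** The strongest reply is that these are boundary slips in an appendix, not a flaw in the design. The safety endpoints in section 2.2.2 are incidences and do not depend on grade. The severity tables are descriptive. The definition of a serious adverse event in section 7.4.1 does not use these grades. A sensible grader, seeing that 38.5°C is already Grade 3, would put 40.0°C at Grade 3 or above. All of this stands, and it limits the point to a minor one.

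It can also be said that shared endpoints recur in Table 6: the acute bronchospasm bands meet at 70% and 50%. That is true, so the vomiting row does not prove that overlap is foreign to the table. It shows only that exclusive bands were available. Recurrence does not tell a grader which cell to use.

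A reader might infer more than the protocol supports:

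- **That a short fever of 39.5°C or more would be graded 1 through Table 7.** This requires stretching the fallback to a listed event, finding no criterion in the guideline, and meeting the Grade 1 conditions of no impact on activities and no treatment. It is not a natural reading.
- **That a febrile subject could receive the second dose.** Section 6.1.1 postpones at an axillary temperature above 37.0°C, whatever the grade.
- **That the erythema row of Table 4 has the same fault.** Its Grade 2 wording on daily life differs from the induration row, but the higher-grade note still yields one grade.
- **That the comparison between groups is biased.** The same tables apply to both arms, and nothing shows that the affected values fall more in one of them.

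**Conclusion.** The point holds as a minor drafting error in safety grading. Read literally, section 11.3 leaves fever of 39.5°C or more for 3 days or less without a grade, and gives two grades to diarrhea at 7 times/day and to nausea at exactly 48 hours. Nothing else in the protocol clearly resolves them.

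The effect is confined to the by-severity tables, at 0.67 points per subject in a 150-subject arm, and rarely to the Grade 3 or higher counts in sections 6.5 and 6.6, where 45 of 300 subjects would be needed and one subject is 0.33 points. Few cases are likely in the experimental group: the Phase I and II event lists in section 1.2.2 name neither fever nor diarrhea, although the same section includes both among the known risks. For the active control, section 3.2.3.1 gives an overall Phase I adverse event rate of 100% without event types, so its frequency cannot be judged. The primary analysis, the sample size and the incidence endpoints are untouched.

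The conclusion rests on the literal text, on calendar-day counting for fever, and on all 300 subjects as the denominator of the 15% rule. A stated rule in the cited guideline could decide which diarrhea cut-off was intended, but would not make the present cells consistent.

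**What to change.** Amend three rows of section 11.3:

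- **Fever:** Grade 3 becomes 38.5 to <39.5°C at any duration, or ≥39.5°C lasting 3 days or less. Grade 4 stays at ≥39.5°C for more than 3 days.
- **Diarrhea:** make the bands exclusive. Use 5–6 for Grade 2 and ≥7 for Grade 3 as the cautious choice, unless the cited guideline shows that 5–7 and >7 was meant.
- **Nausea:** Grade 2 becomes 24 to <48 hours; Grade 3 stays at 48 hours or more.

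Apply the same cut-offs to every subject in both groups, and put them in the eCRF completion guidelines.

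The cost is a wording amendment submitted to the IRB under section 10.1.4 and the matching eCRF text. No visits, samples or subjects are added. A few events may be graded higher than a grader might have chosen under the present text.
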